Evaluation of the Effectiveness of Vestibular Rehabilitation With Virtual Reality Systems in Individuals With Visually Induced Motion Sickness

NCT: Pending

Document Date:
June 2025

Study Protocol

A test protocol was developed to provide vestibular rehabilitation using virtual reality systems for individuals with visually induced motion sickness (VIMS).

The study protocol consists of three phases:

In the first phase, all participants underwent the Simulator Sickness Questionnaire (SSQ) and static posturography tests, including Balance Screening and Limit of Stability assessments, prior to the initial evaluation. Subsequently, participants were exposed to 5 - minute YouTube open-access 360° virtual reality (VR) videos with varying difficulty levels determined beforehand. The initial evaluation lasted 30 minutes and was structured as follows: 5 minutes of easy stimulation followed by 5 minutes of rest, 5 minutes of moderate stimulation followed by 5 minutes of rest, and 5 minutes of high stimulation followed by 5 minutes of rest. During each 5-minute stimulation, heart rate and balance screening tests were measured at minutes 1, 3, and 5. After the total 15 minutes of stimulation, final measurements including the SSQ, balance screening, and Limit of Stability tests were repeated (Table 1).

Table 1 Phase I: Initial Evaluation Protocol

Phase I	Easy Level	Moderate Level	High Level
Stimulus			
Pre-stimulation	Walking Video Simulator Sickness Questionnaire (SSQ) Balance Screening Limit of Stability	Driving Video Simulator Sickness Questionnaire (SSQ) Balance Screening Limit of Stability	Drone Video Simulator Sickness Questionnaire (SSQ) Balance Screening Limit of Stability
Order of Stimulation	During each 5-minute stimulation, Balance Screening (BS) and heart rate measurements were taken at minutes 1, 3, and 5.	During each 5-minute stimulation, Balance Screening (BS) and heart rate measurements were taken at minutes 1, 3, and 5.	During each 5-minute stimulation, Balance Screening (BS) and heart rate measurements were taken at minutes 1, 3, and 5.
Post-stimulation	Simulator Sickness Questionnaire (SSQ) Balance Screening Limit of Stability	SSQ	SSQ
Qualitative Data Collection Tool	SSQ	SSQ	SSQ

Quantitative Data Collection Tool	Balance Screening Heart Rate Monitor	Balance Screening Heart Rate Monitor	Balance Screening Heart Rate Monitor
-----------------------------------	---	---	---

In the second phase, a four-week rehabilitation program was designed for individuals with VIMS, consisting of two 1-hour sessions per week (Table 2). The prepared rehabilitation program was administered to the study group using virtual reality systems.

Table 2 4-week rehabilitation program

	Seans	Seans
Two sessions per week	6 × 5-minute easy stimulations (with 5-minute rest periods between stimulations)	4 × 5-minute easy stimulations plus 2 × 5-minute moderate stimulations (with 5-minute rest periods between stimulations)
Two sessions per week	6 × 5-minute moderate stimulations (with 5-minute rest periods between stimulations)	2 × 5-minute easy stimulations plus 4 × 5-minute moderate stimulations (with 5-minute rest periods between stimulations)
Two sessions per week	6 × 5-minute moderate stimulations (with 5-minute rest periods between stimulations)	3 × 5-minute moderate stimulations plus 3 × 5-minute high stimulations (with 5-minute rest periods between stimulations)
Two sessions per week	6 × 5-minute high stimulations (with 5-minute rest periods between stimulations)	30-minute final evaluation session: 1 × 5-minute easy stimulation + 2 × 5-minute moderate stimulations + 3 × 5-minute high stimulations

In the third phase, following the rehabilitation program, participants were reassessed using the Simulator Sickness Questionnaire (SSQ), and static posturography tests, including Balance Screening and Limit of Stability assessments, were repeated.

Statistical Analysis

The data obtained in this study were analyzed using Statistical Package for Social Sciences (SPSS) for Windows, version 25.0. Descriptive statistical methods (number, percentage, minimum-maximum values, mean, and standard deviation) were used to summarize the data. The normality of the data was assessed using skewness and kurtosis values. For normally distributed data, independent-samples t-tests were used to compare quantitative variables between two independent groups, and paired-samples t-tests were used to compare two dependent groups. Pearson correlation was applied to examine relationships between numerical variables. For data that were not normally distributed, the Friedman test was used for comparisons of more than two dependent groups. When a significant difference was found, the adjusted Bonferroni test was used to identify the group causing the difference. Spearman correlation was used to assess relationships between numerical variables. The homogeneity of categorical variables was examined using the Chi-square test.

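### The final evaluation session in Table 2 gives twice the stimulation of the Phase I evaluation (30 vs 15 minutes; high level 15 vs 5), so measures taken after the two sessions are not like for like

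*Combined protocol and SAP*

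**What the plan says.** **Initial evaluation (Study Protocol, first phase).** The text states: "The initial evaluation lasted 30 minutes and was structured as follows: 5 minutes of easy stimulation followed by 5 minutes of rest". The moderate and high levels follow the same pattern. The post-tests are placed at the end: "After the total 15 minutes of stimulation, final measurements including the SSQ, balance screening, and Limit of Stability tests were repeated". The same three tests are also taken before stimulation. Table 1 is laid out differently: under post-stimulation it shows the SSQ (Simulator Sickness Questionnaire) for every level, and Balance Screening and Limit of Stability only in the easy column.

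**Programme (second phase, Table 2).** The programme is described as "consisting of two 1-hour sessions per week" over four weeks, given to the study group. The last of its eight sessions is the "30-minute final evaluation session: 1 × 5-minute easy stimulation + 2 × 5-minute moderate stimulations + 3 × 5-minute high stimulations". The other seven sessions carry the note "with 5-minute rest periods between stimulations"; this one does not.

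**Reassessment (third phase).** The SSQ, Balance Screening and Limit of Stability are repeated: "following the rehabilitation program, participants were reassessed". No stimulus, interval or timing relative to the last session is given.

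**Statistical Analysis.** For normally distributed data, "paired-samples t-tests were used to compare two dependent groups". The section does not name the time points to be paired. It also plans independent-samples t-tests between two groups.

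**The concern.** Table 2 itself calls its last session an evaluation, which makes it the natural counterpart of the initial one. Both are labelled 30 minutes, and this hides the difference: the first figure includes 15 minutes of rest, while the second already equals six 5-minute stimulation blocks.

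A before-after comparison of a provoked response needs the same provocation both times. If it differs, the change score combines what the training did with what the heavier stimulus did. A paired t-test cannot separate the two, and nothing in the analysis section adjusts for it. The outcomes exposed to this are the SSQ, Balance Screening and Limit of Stability values taken at the end of each session.

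The same problem could reach the between-group comparison. Only the study group is said to receive the programme, and no Phase II or III schedule is described for a comparison group. If that group did not have the same final session, the two groups would be tested after different stimulation.

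**Working it through.** **Inputs.** The Phase I blocks and rests come from the first-phase text. The final-session blocks come from the last cell of Table 2. Every block lasts 5 minutes.

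**The plan's own figures first.** Initial evaluation: stimulation 5 + 5 + 5 = 15 min; rest 3 × 5 = 15 min; total 30 min. This reproduces both stated figures, 15 minutes of stimulation and a 30-minute evaluation.

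**Final session.** Stimulation 1 × 5 + 2 × 5 + 3 × 5 = 5 + 10 + 15 = 30 min.

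| Stimulation (min) | Initial | Final | Ratio |
|---|---|---|---|
| Easy | 5 | 5 | 1.0 |
| Moderate | 5 | 10 | 2.0 |
| High | 5 | 15 | 3.0 |
| Total | 15 | 30 | 2.0 |
| High-level share | 5/15 = 33% | 15/30 = 50% | |

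**Does the missing rest note change this?** With no rests the final session takes 30 min by the clock. With rests between blocks it takes 30 + 5 × 5 = 55 min, and with a rest after each block 30 + 6 × 5 = 60 min. The last two fit the stated one-hour sessions. Stimulation is 30 min on every reading, so the doubling does not depend on the rests.

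**Which comparisons are affected?** The plan leaves two readings open.

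- *Phase III tests follow the final session.* Each result then comes after 30 minutes of stimulation and would be set against a Phase I value taken after 15. Training and stimulus are mixed.
- *Phase III tests are taken at rest.* No stimulus precedes them, so the mismatch has no effect. The like-for-like baseline is then the Phase I set taken before stimulation. Pairing with the post-stimulation set would compare rest with a provoked state.

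**Direction on the first reading.** The videos are graded from easy to high. If a heavier stimulus provokes more symptoms and sway, the final values are pushed up and the improvement looks smaller. The documents contain no data on response by dose, so no size can be given.

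**The case against.** The strongest reply is that the documents never say the Phase III tests follow this session. Table 2 belongs to the second phase; the third phase comes after the programme and names no stimulus. It also omits heart rate, which Phase I measured during stimulation. That fits a reassessment at rest. A session that ends a graded programme may reasonably be heavier than a first exposure, and the analysis section does not say that this session feeds any comparison.

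Much of this stands. The bias in the Phase III results is conditional. The omission of heart rate is not decisive, because the three Phase III tests are also the Phase I post-stimulation set, and Table 2's own label points the other way. If the session is only training, the plan describes no stimulated final evaluation comparable with Phase I, and it should say so.

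Two further points stand. Table 1 can be read as an SSQ after every level, in which case the Phase I counterpart is not simply one value after 15 minutes. That layout may, however, be a product of text extraction. The documents are also mostly in the past tense, so a redesign may come too late.

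A reader might infer more than the text supports:

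- *That the trial's before-after result is biased.* The timing of the Phase III tests is unstated, and one of the two readings removes the bias.
- *That the final session ran without rests.* One absent note in a table cell is thin evidence against the stated one-hour sessions.
- *That readings during individual blocks can be matched between the sessions.* Phase I took "heart rate and balance screening tests were measured at minutes 1, 3, and 5", but nothing says this was done in the final session, or in what order its blocks ran.

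**Conclusion.** The concern holds in a limited form. It is certain from the text that the final evaluation session does not repeat the initial one: 30 against 15 minutes of stimulation, and 15 against 5 minutes at the high level. Measures taken after these two sessions are therefore not comparable as measures of training.

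Whether this touches the reported Phase III results depends on when those tests were taken, which the plan does not state. If they followed the final session, benefit would probably be understated, assuming that heavier stimulation provokes more symptoms; the amount is unknown. If they were taken at rest, this bias is absent and what remains is to name the pre-stimulation set as the baseline.

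This is a worthwhile improvement at small cost. It does not show that the trial's conclusions are wrong.

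**What to change.** **If data are still to be collected.** Make the final evaluation repeat Phase I: one easy, one moderate and one high block in that order, with 5 minutes of rest after each. Take the SSQ, Balance Screening and Limit of Stability before and after. Do this in the study group and in any comparison group. State that this session is the Phase III assessment. Pair pre-stimulation with pre-stimulation values and post-stimulation with post-stimulation values. Clarify whether the SSQ is taken after each level, as Table 1 suggests, or only at the end, and do the same on both occasions.

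*Cost.* Programme stimulation is now 7 × 30 + 30 = 240 min and would become 7 × 30 + 15 = 225 min, a fall of 15/240 = 6.25%. At most one further set of tests is needed, with no extra visit for the study group. The cost for a comparison group cannot be given, because its schedule is not described; if it has no final session at present, it would need one of 30 minutes.

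**If data already exist.** State when the Phase III tests were taken, whether rests were given in the final session, and what any comparison group received. Where Phase III tests were taken at rest, compare them with the Phase I pre-stimulation set. Otherwise report end-of-session comparisons as made after 15 against 30 minutes of stimulation, with a sentence on the limitation. Do not switch the main outcome on this account. The cost is a few sentences, but the mismatch cannot then be removed from the end-of-session results.

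### The plan specifies no between-group comparison of Phase III outcomes that uses the Phase I value, and the comparator such a comparison needs is only implied

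*Combined protocol and SAP*

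**What the plan says.** The title sets out to evaluate effectiveness. The only analysis text is the one paragraph under Statistical Analysis. Where a variable passes the normality check, the plan is that "independent-samples t-tests were used to compare quantitative variables between two independent groups, and paired-samples t-tests were used to compare two dependent groups". For the rest, "For data that were not normally distributed, the Friedman test was used for comparisons of more than two dependent groups", followed by a Bonferroni-type adjustment. Correlations and a chi-square test complete the list. No test is attached to a named outcome or phase, and no change score, covariate or group-by-time term appears.

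The Study Protocol shows which data exist:

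- **First phase, before stimulation:** all participants had the SSQ and static posturography, including "Balance Screening and Limit of Stability assessments, prior to the initial evaluation".
- **First phase, after stimulation:** "final measurements including the SSQ, balance screening, and Limit of Stability tests were repeated".
- **Second phase:** "a four-week rehabilitation program was designed for individuals with VIMS", and "The prepared rehabilitation program was administered to the study group using virtual reality systems".
- **Third phase:** "participants were reassessed using the Simulator Sickness Questionnaire (SSQ), and static posturography tests", with Balance Screening and Limit of Stability again included.

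The existence of a second group is inferred from the reference to a study group in the second phase and to two independent groups in the analysis paragraph. The documents do not say who is in it, whether its members have VIMS, how they were allocated, or whether they were reassessed in the third phase.

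**The concern.** A reader cannot tell which comparison is meant to carry the effectiveness conclusion, and the readings open under the listed tests are not equally good.

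- **Within-group test.** A significant paired or Friedman result in the study group cannot separate the programme from retest practice or regression to the mean.
- **Independent t-test on Phase III values alone.** This ignores a measurement already taken. It is less precise than ANCOVA whenever the Phase I value predicts the Phase III value to a useful degree. If the groups were not randomised, a baseline difference can also pass for an effect.
- **Non-normal outcomes.** Friedman is a within-subject test. If an outcome fails the skewness and kurtosis check, the plan offers no way to compare the groups on it.

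At stake are false credit to the programme in the first case, and in the second a missed effect or a biased one.

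**Working it through.** **Inputs.** The documents give no sample size, SD, significance level, effect size or correlation, so there is no planned figure to reproduce. Everything below is an illustration on assumed inputs: two-sided 5%, n = 20 per group (10 to 30 where shown), outcome SD 1 in both phases, and Phase I to Phase III correlation r = 0.3, 0.5 or 0.7.

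**1. Within-group test when the programme adds nothing.** Both groups change by the same amount d, in SDs of the paired differences. The paired t-test has noncentrality d√n on n − 1 df.

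- d = 0.3: 0.3 × √20 = 1.34, significant in 25% of trials (14% at n = 10, 36% at n = 30).
- d = 0.5: 0.5 × √20 = 2.24, significant in 56% (29% to 75%).

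**2. Power for a true 0.6 SD effect in comparable groups.** The noncentrality is (0.6/s)√(n/2), with s = 1 for Phase III only, s = √(2(1 − r)) for the change score and s = √(1 − r²) for ANCOVA. The df are 2n − 2, and 2n − 3 for ANCOVA. At n = 20, √(n/2) = 3.162, so Phase III only has noncentrality 0.6 × 3.162 = 1.90. For ANCOVA at r = 0.7 it is 1.90/√0.51 = 2.66.

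| n = 20 per group | r = 0.3 | r = 0.5 | r = 0.7 |
|---|---|---|---|
| Phase III only | 46% | 46% | 46% |
| Change score | 35% | 46% | 67% |
| ANCOVA | 49% | 57% | 73% |

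For n = 10 and n = 30, Phase III only gives 25% and 63%. ANCOVA gives 26/31/43% and 67/75/89%. The change score is worse than Phase III only when r is below 0.5, because 2(1 − r) then exceeds 1. The precision gain therefore belongs to ANCOVA and not to baseline use in general.

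**3. False positives from a baseline gap, relevant only without randomisation.** Take no effect and a 0.5 SD gap in Phase I.

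- *Gap persists.* The spurious difference is 0.5 for Phase III only, 0 for change and 0.5(1 − r) for ANCOVA.
- *Gap regresses to r × 0.5.* The spurious difference is 0.5r for Phase III only, −0.5(1 − r) for change and 0 for ANCOVA.

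Rejection rates at n = 20 (simulated, 200,000 runs per cell), for r = 0.3/0.5/0.7:

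| | Gap persists | Gap regresses |
|---|---|---|
| Phase III only | 34% at each r | 7.5/12/19% |
| Change score | 5% | 15/12/9% |
| ANCOVA | 19/14/9% | 5% |

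The change score holds its level in the first case and ANCOVA in the second. Neither does so in both. Agreement between them proves nothing either: if a 0.5 SD gap widens to 0.7 SD with no effect and r = 0.5, change is biased by 0.7 − 0.5 = 0.20 and ANCOVA by 0.7 − 0.5 × 0.5 = 0.45, in the same direction.

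**4. Which values are comparable.** The first phase yields two candidates for the Phase I value, before and after three 5-minute stimulations (15 minutes). The third-phase text does not say when its values were taken relative to stimulation. The final evaluation session in Table 2 has 1 + 2 + 3 = 6 stimulations of 5 minutes (30 minutes). If Phase III values followed that session, a change score does not compare like with like, and a comparator without the programme may not have had the session at all.

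**The case against.** The strongest reply is that the plan is underspecified and not shown to be wrong. The general wording about quantitative variables could cover t-tests on change scores. Nothing says that effectiveness rests on the paired test or on Phase III values alone. That stands. A reader might infer that the baseline was ignored or that the conclusion was drawn from within-group p-values. The documents do not show either, and the figures above describe what those analyses would do, not what was done.

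Second, the missing comparator comes before any choice of model. If the second group does not have VIMS, or was not reassessed, no ANCOVA answers the question. That also stands, and it sets the order of the fix.

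Third, under randomisation the Phase III-only t-test keeps its 5% error rate overall, and only precision is lost. Correct: a reader might take the 34% as this trial's false-positive rate, but it applies only to a non-randomised comparison with an assumed gap. The documents neither state nor exclude randomisation.

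What remains is that no listed test is committed to a between-group comparison using the Phase I value, and that the non-normal branch has no between-group test.

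**Conclusion.** The gap in specification is certain from the text. Its consequence cannot be sized from the documents. On the assumed inputs at 20 per group, it ranges from a few points of lost power (46% against 49% at r = 0.3) to a large loss (46% against 73% at r = 0.7). If a within-group test were the basis, a modest shared change would look like success in a quarter to a half or more of trials. Bias from a baseline gap is an additional risk only if allocation was not randomised.

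It would go too far to conclude that the trial has a VIMS control group that was analysed badly, or that it has none. The documents settle neither. The point should be fixed because, where a reassessed comparator exists, the better analysis uses data already collected. Where none exists, the stated aim exceeds what the design can support.

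**What to change.** 1. State who the second group is, whether they have VIMS, how they were allocated, and whether they were reassessed in the third phase.
2. If it is a reassessed VIMS group without the programme, base the effectiveness conclusion on ANCOVA of the Phase III value on group and the Phase I value of the same measure. Report the adjusted difference with a 95% CI. Use a rank-based or robust version if residuals are clearly non-normal.
3. If allocation was not randomised, show the between-group difference in change beside it. Treat disagreement as unresolved confounding, and state that agreement does not rule confounding out.
4. State which Phase I value is used (before or after stimulation) and when Phase III values were taken relative to stimulation, including the final evaluation session in Table 2. The change score needs matching conditions; the ANCOVA covariate does not strictly need them.
5. Treat the paired and Friedman tests as descriptive.
6. If there is no such comparator, report uncontrolled pre/post change and do not claim effectiveness.
7. The analysis text is in the past tense. If the analysis is already done, label the added model post hoc.

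Cost: where the comparator was reassessed, this takes SAP wording and one SPSS model per measure, with no new visits. Where it was not, no analysis can supply the comparison and the cost is a weaker conclusion. In either case within-group p-values lose their headline role, and a post hoc model carries less evidential weight than a prespecified one.

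### Skewness and kurtosis choose the test with no cut-off, three of six comparison types have no named test, no baseline adjustment is stated between groups, and Friedman cannot test level by minute

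*Combined protocol and SAP*

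**What the plan says.** The Statistical Analysis section is one paragraph in the past tense. On how a test is chosen it says: "The normality of the data was assessed using skewness and kurtosis values". It gives no threshold and does not say whether the check is made per group, on pooled data or on differences.

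For data judged normal, "independent-samples t-tests were used to compare quantitative variables between two independent groups", and paired t-tests serve two dependent measurements. For data judged non-normal, the one comparison test is this: "For data that were not normally distributed, the Friedman test was used for comparisons of more than two dependent groups". The follow-up reads: "When a significant difference was found, the adjusted Bonferroni test was used to identify the group causing the difference". Correlations have a test under either label and Chi-square covers categorical variables, so neither is at issue here.

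The Study Protocol section gives the data structure:

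- **Phase one.** At the start, "all participants underwent the Simulator Sickness Questionnaire (SSQ) and static posturography tests". Three videos follow in a fixed order: an easy block first, then "5 minutes of moderate stimulation followed by 5 minutes of rest, and 5 minutes of high stimulation followed by 5 minutes of rest". Heart rate and Balance Screening are read at minutes 1, 3 and 5 of each block.
- **Phase two.** "The prepared rehabilitation program was administered to the study group using virtual reality systems". The comparator is not described, nor is how the groups were formed.
- **Phase three.** SSQ, Balance Screening and Limit of Stability are measured again.

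**The concern.** The study title promises an evaluation of effectiveness, so readers will look first for the between-group and pre/post SSQ results. If SSQ scores are skewed, the section names no test for either. Whether they count as skewed depends on a threshold that cannot be looked up. A reader could not tell which test lies behind a reported p-value, or whether it was chosen after the data were seen.

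Two further losses concern method rather than reporting. Baseline values exist for the three main measures, but no use of them is stated in the group comparison. And the in-stimulation readings form a grid of level by minute, whose natural question is whether the response builds up differently at harder levels. The named test cannot answer that formally.

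**Working it through.** The documents state no sample size, alpha, SD, correlation or power, so there is no planned figure to reproduce. Step 1 is a count from the text. The later steps use assumed inputs, marked as such.

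**Step 1. Coverage.** 3 comparison types × 2 labels = 6 cases, of which 3 have a named test.

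| Comparison | Normal | Non-normal |
|---|---|---|
| Two independent groups | independent t | none named |
| Two dependent measurements | paired t | none named |
| More than two dependent measurements | none named | Friedman |

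**Step 2. Effect of the missing cut-off.** Assumed rule: bias-corrected skewness and excess kurtosis both within ±c. Assumed n = 20; 20,000 simulated samples.

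| c | 1 | 1.5 | 2 |
|---|---|---|---|
| Normal data labelled non-normal | 24% | 8% | 4–5% |
| Log-normal data (log-SD 0.7) labelled normal | 24% | 47% | 54% |

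**Step 3. Value of baseline if groups are comparable.** Relative to a post-score t-test, the variance factor f is 1 − ρ² for ANCOVA and 2(1 − ρ) for change scores. If the post-score test has 80% power at two-sided 0.05 (assumed), power becomes Φ((1.960 + 0.842)/√f − 1.960).

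| ρ (assumed) | ANCOVA f | ANCOVA power | Change f | Change power |
|---|---|---|---|---|
| 0.3 | 0.91 | 83.6% | 1.40 | 65.8% |
| 0.5 | 0.75 | 89.9% | 1.00 | 80.0% |
| 0.7 | 0.51 | 97.5% | 0.60 | 95.1% |

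The unstated choice between post and change score therefore matters in its own right.

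**Step 4. If groups were not randomised.** Suppose they differ by δ at baseline and neither truly changes. The expected group difference is δ on post scores, δ(1 − ρ) under ANCOVA and 0 on change scores. With ρ = 0.5, δ = 0.5 to 1.0 SD and 20 per group (assumed), the simulated false-positive rates are 34–88% for the post-score t-test, 13–35% for ANCOVA and 4–5% for the change-score t-test. How the groups were formed therefore decides which baseline method should lead.

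**Step 5. Friedman on the 3 × 3 readings.** The schedule allows series of 3 (minutes within a level, levels, or averages) or 3 × 3 = 9. The Bonferroni pairs are 3 × 2/2 = 3 or 9 × 8/2 = 36, giving 0.05/3 = 0.0167 or 0.05/36 = 0.0014 per pair at an assumed alpha of 0.05. The table shows the percentage of significant results for n = 20, normal readings, common correlation 0.5 and 0.4 SD steps (all assumed).

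| Friedman series | Level effect only | Minute effect only | Interaction only |
|---|---|---|---|
| Nine readings | 99% | 99% | 93% |
| Per-level averages | 99.5% | 5% | 5% |
| Per-minute averages | 5% | 99.6% | 5% |
| Minutes within each level | not run | 74–75% | about 75% in two affected levels, 5% in the third |

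Nine readings give a significant result without showing which factor caused it. Averages separate the main effects but miss the interaction. Within-level tests show the pattern but do not test whether the levels differ. A two-factor repeated-measures ANOVA on the same data detects the interaction in 98% of runs, with absent terms at about 5%. At 0.2 SD steps it detects the interaction in 47%.

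**Step 6. Does the replacement hold up?** Minutes 1, 3 and 5 lie inside one video block, so they may correlate more with each other than across blocks. With within-block correlation 0.6–0.8 against 0.5 between blocks (assumed) and no true effect, a mixed model with a participant effect alone falsely finds a level effect in 13–32% of runs. Its interaction test becomes very conservative (error 2.5% down to under 0.1%). Two-factor repeated-measures ANOVA keeps the level test at 5%.

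**The case against.** The strongest reply is that the section reports tests already used, so the empty cases may never have arisen. On that view a sentence naming the cut-off, outcome form and test per outcome would be enough, and replacing the methods is preference. The first part stands: the document does not show that any empty case occurred. But a sentence of disclosure would not bring the baseline into the group comparison or supply a test of level by minute.

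Three stronger readings are tempting, and the documents do not support them.

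- **That the plan delivers 40% power on a skewed SSQ.** With log-SD 1.0, a true halving, correlation 0.5 and 20 per group, a t-test on every sample has 40% power, Mann-Whitney 55% and rank ANCOVA 64–65%. Within group at n = 20, paired t has 58% and Wilcoxon 75%. But the plan restricts t-tests to data judged normal. Under the Step 2 rule, both groups pass in only about 1–13% of such two-group samples, and the t-test then has 61–71% power. In the rest no test is named. The 40% and 58% describe a rule that the plan does not state. Nor is the t-test invalid here: its simulated type I error on skewed data is 3.5%.
- **That Friedman was run over nine readings with 36 follow-up pairs.** The text does not name the series. Minutes within each level is an equally natural reading and is more informative. Friedman on a derived within-level change could compare levels, but no such derived score is mentioned.
- **That baseline-adjusted ANCOVA is the right default.** Step 4 shows that this depends on randomisation, which the documents do not mention.

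**Conclusion.** The point holds as a combination of missing specification and improvable method. It should be corrected but does not invalidate the study. Four facts rest on the text alone: no cut-off, three of six comparison types without a named test, no stated baseline adjustment or outcome form, and an unnamed Friedman series. Friedman's inability to test the interaction on the readings or their averages follows from its being a one-factor test.

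The numerical sizes all rest on assumed sample sizes, distributions and correlations. They show that the cut-off and the use of baseline can matter materially; they do not measure what this trial lost. Any advantage of ANCOVA requires comparable groups. Any advantage of the two-factor analysis requires an error structure that respects the blocks.

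**What to change.** Set the method by outcome and drop the normality check as the selector.

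1. **Between groups.** State how the groups were formed and which measurements the comparator has.
   - Randomised, with baseline and post scores: baseline-adjusted ANCOVA for Balance Screening and Limit of Stability, rank ANCOVA for SSQ.
   - Not randomised: compare change scores (Mann-Whitney on change for SSQ), report ANCOVA alongside, and state that neither removes systematic group differences.
   - Comparator with phase-one data only: Mann-Whitney for SSQ, t-test for the others.
2. **Within group.** Wilcoxon signed-rank for pre/post SSQ.
3. **Nine in-stimulation readings.** Use a level × minute repeated-measures ANOVA with a sphericity correction, or a mixed model with participant and level-within-participant random effects (not a participant effect alone). Add Bonferroni-adjusted contrasts and a rank-based sensitivity analysis.
4. **Interpretation.** State that level is confounded with cumulative exposure because the order is fixed; no model removes this.

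If the analysis is complete, as the past tense suggests, state the test and series used for each outcome and report the methods above as sensitivity analyses.

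Cost: no new data. It needs SAP wording or, if the analysis is finished, a re-run on stored data and a short addendum. The model for the in-stimulation readings is slightly more complex to report.
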